### **3.m.1 Biannual Reporting**

The study team will complete biannual reports that have been approved by the SO as well as NIAMS personnel prior to starting study recruitment. Open session Data and Safety Monitoring reports will detail enrolment for the previous 6-month period as well as the overall study. We will report screening rates/ failures, actual vs expected enrollment, participant demographics, participant enrollment status, key baseline participant characteristics, study duration for participants, missed visits, CRF, adverse events, deaths, unanticipated problems and protocol deviations. The reports can be found in Appendix and will be electronically mailed to the SO, [name], and NIAMS on a biannual basis. Final closeout reporting will entail the same detailed information for the final study period as well as the entire study. Final closeout reporting documents can be found in Appendix and will be electronically mailed to the SO, [name], and NIAMS.

### **3.O Data Management**

Epi Info, which is a product of the Centers of Disease Control, will be used to enter outcomes data and export data to SPSS which will be used for data analysis.

**Data tracking** – The status of enrollment will be tracked with Epi Info. A separate telephone call log will be kept with the number of people that contact the study team who are interested in the study. We will also keep a log of encounters the study team may have with patients at the clinic. We will keep data indicating how many patients screen out of the study over the telephone or in the clinic due to exclusion criteria or disinteresting

participating. We will collect the number of patients that complete the initial consenting process and screen into the study following the screening visit to the laboratory. Finally we will determine how many people that screen into the study are randomized into a treatment condition.

**Data Entry** – Data will be entered from electronic files or paper surveys. Outcome measures will be cut and pasted from excel or collection software into Epi Info to minimize data entry error. Two separate investigators will calculate paper questionnaire scores with a Microsoft Excel spreadsheet to minimize mathematical error prior to entry. All outcome measure data will be entered into separate spreadsheets by two individual investigators.

**Data Editing** – Data means and standard deviations will be calculated each month and crossed- referenced between databases for each investigator. If means are different investigators will look to determine which outcomes differ. In the case that investigators cannot come to a consensus on the correct outcome measure, [name] will act as an arbiter.

**Updating** – Data may need to be updated due to an error in data entry. After the incorrect data point has been determined the investigator in charge of that data set should be notified and the Signature Log should be signed indicating who changed data in the spread sheet, what data was changed, for what reason was it changed as well as the time and date it was changed. A new database with the current date should be created. The previous database with the error should not be deleted.

**Reporting** – Investigators will report the number of patients that were recruited each week at the study meetings. Investigators will anticipate 4 and 8 week follow–up testing in scheduling laboratory visits and report data that was not collected for follow-up time points due to patient drop outs. Report

**Statistical Analyses** – All data will be reported directly from Epi Info to SPSS.

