Informed Consent & Scheduling	[name] [name] [name]	These personnel will be in charge of consenting each patient, explaining the study to each participant and acquiring written informed consent from each participant. [name] and [name] will schedule patients for: 1) screening/baseline sessions, 2) the first physical therapy session (all other physical therapy sessions will be scheduled by the the clinic staff), 3) follow-up test one, and 4) follow-up test two.
Screening	[name] [name] [name] [name]	Screening will consist of central activation ratio and WOMAC score testing.
Collection of Data (Baseline and Follow-up Measures)	[name] [name]	These follow-up tests will be conducted by only the blinded investigators at baseline, follow-up one (4 weeks) and follow-up two (8-weeks).
Education on TENS unit and Sham TENS with Patients (Available to answer questions throughout study)	[name] [name] [name]	These investigators will be unblinded and will be in charge of teaching patients how to utilize the active TENS and Sham TENS units immediately prior to the first physical therapy session. Additionally, phone numbers for [name] and [name] will be provided if further assistance is needed.
Delivery of Physical Therapy Intervention	[name] [name] [name] [name] [name] [name]	Patients will be scheduled to work independently with one of these clinicians. All clinicians will conduct therapeutic exercises according to the guidelines provided in g.1 .
Study Compliance & Accountability	[name]	[name] will evaluate study compliance for 1) randomization, follow-up testing, IRB Compliance, and compliance of treatment protocols as described in section 3.m
Randomization of Patients	[name] [name] [name]	The randomization scheme will be developed by [name] and [name] will determine each patient's group from a sealed envelopes. [name] will be unblinded and in charge of the randomization lists.
Data Entry, Error Identification and Correction	[name] [name] [name]	[name] and [name] will perform double data entry. [name] will calculate means and standard deviations separately for all outcomes measures. [name] will determine were potential errors are found and [name] (Blinded

		Investigator) will be consulted to determine the correct outcome measure.

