### **Western Ontario and McMaster University Osteoarthritis (WOMAC) Index**

The Participant will be provided a quiet room with a desk and access to an investigator. The participant will fill out all subsections of the WOMAC (Pain, Stiffness and Function). The investigator will score the function section by adding the numbers associated with the various answers. A WOMAC Function score of 23 or higher indicates that the participant is experiencing enough dysfunction to be included in the study. The participant will then undergo quadriceps central activation ratio testing.

**Neuromuscular Activation:** We will assess quadriceps central activation ratio as a representative variable of lower extremity neuromuscular activation. Quadriceps central activation ratio has been demonstrated to be significantly decreased in knee OA compared to healthy, matched controls, and we have reported acceptable measurement reliability ( $ICC_{2,k} = 0.85$ ) over 4 weeks. Quadriceps central activation ratios will be collected as previously reported by the PI using an automated triggered method to improve reliability of this technique.

**Gait Biomechanics:** Peak sagittal plane knee kinematics and kinetics will be collected during the first 50% of stance phase and processed in our 3-dimensional, 10-Camera (Vicon) motion capture laboratory. Gait will be collected at a self-selected speed; speed at pre- and post-tests will be used as a time-dependent covariate

**Physical Function:** Physical function will be measured with the three core performance-based tests (30-s chair-stand test, 40 m fast-paced walk test, a stair-climb tests) endorsed by the Osteoarthritis Research Society International guidelines.

**Physical Activity:** Self-reported physical activity will be quantified using the Physical Activity Scale for the Elderly (PASE), which is a valid tool to assess self-reported participation in physical activities of varying intensities.

**The Self-Efficacy for Physical Activity (SEPA):** The SEPA scale will be used to assess the respondents' confidence in their ability to be physically active despite common barriers (adverse weather, lack of time, when tired, in a bad mood, or on vacation). The SEPA has demonstrated good internal consistency and construct validity as well as acceptable retest reliability (0.9) over 2 weeks.

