### **3.p.2 Data and Forms Check**

Data will be checked using several methods including the data entry, data editing and data updating that have been outlined in section 3.O. We will use a double data entry technique and clean data as it becomes available in the Info Track databases. Means and standard deviations will be checked weekly to determine that the double data entry databases provide the same values for central tendency and variability for all outcome measures. Two separate investigators, using a Microsoft Excel calculation spreadsheet, will calculate outcomes from forms. Versions of forms and spreadsheets will be evaluated every time data is entered into the spreadsheets or when forms are provided to the patients.

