### **3.p.3 Data Double Entry**

We will use a double data entry technique and clean data as it becomes available in the Info Track databases. Means and standard deviations will be checked weekly to determine that the double data entry databases provide the same values for central tendency and variability for all outcome measures. Two separate investigators, using a Microsoft Excel calculation spreadsheet, will calculate outcomes from forms.

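### Double entry is reconciled only through means and SDs, so values filed under the wrong participant can pass the check unseen

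*Combined protocol and SAP*

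**What the plan says.** Section 3.O (Data Entry) provides for independent duplicate entry: "All outcome measure data will be entered into separate spreadsheets by two individual investigators". The route into the database is copying from files: "Outcome measures will be cut and pasted from excel or collection software into Epi Info to minimize data entry error". No match on participant ID is stated for that step.

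Reconciliation is described in four places, each time through summary statistics:

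- 3.O, Data Editing: "Data means and standard deviations will be calculated each month and crossed- referenced between databases for each investigator". The next step is conditional: "If means are different investigators will look to determine which outcomes differ". Taken literally, only a difference in means starts the search.
- 3.p.2: "Means and standard deviations will be checked weekly to determine that the double data entry databases provide the same values".
- 3.p.3 (Data Double Entry): the weekly check is that the "double data entry databases provide the same values for central tendency and variability for all outcome measures".
- 3.c, staff roster, row on data entry and error correction: one person "will calculate means and standard deviations separately for all outcomes measures", and errors are identified from there.

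The interval is monthly in 3.O and weekly in 3.p.2 and 3.p.3. No section gives the precision at which the summaries are compared, or says which of the two databases is exported to SPSS.

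**The concern.** The purpose of double entry is to show where two independent records of the same item disagree. Comparing column summaries gives up most of that. Mean and SD are functions of the set of values in a column, not of their assignment to participants. Suppose one database has two participants' values exchanged, or a pasted column out of step with its IDs. The summaries then agree exactly, and under the stated rule nobody looks further. Cut-and-paste entry makes this kind of error plausible.

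If the misaligned database is the one analysed, three things can happen:

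- A swap across arms shifts the arm contrast.
- A random re-sort across arms pulls the contrast toward zero in expectation.
- A swap within an arm leaves the arm mean, and the arm's mean change, as they were. It does break the link between a participant's baseline, follow-up and covariate values. This inflates the variance of change scores and weakens covariate adjustment. The gait analysis depends on that link, since walking "speed at pre- and post-tests will be used as a time-dependent covariate" (Gait Biomechanics, under 3.i.2).

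Errors that alter a value usually alter the mean or SD and are outside this point.

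**Working it through.** The plan gives no figure to reproduce here, so the check has two parts: whether the rule can fail, and how much a failure would matter.

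**Inputs from the documents.** N = 90 (3.e.1); three groups, blocks of 6 (3.g.1).

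**Assumptions.** 30 per arm (the allocation ratio is not stated); outcome SD 8 to 12; swapped values d = 10 or 20 apart; baseline/follow-up correlation r = 0.5 to 0.8; true effect 0.8 SD for the power figures.

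**1. Invariance.** The sums of x and of x² are unchanged by any permutation, so mean and SD are too. On a simulated column of 90 values:

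| Error in one database | Change in mean and SD | Wrong cells | Found by mean/SD | Found by ID-keyed comparison |
|---|---|---|---|---|
| Two participants swapped | 0 | 2 | 0 | 2 |
| Column shuffled | 0 | 89 | 0 | 89 |
| Column sorted | 0 | 89 | 0 | 89 |

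**2. One swap.** Possible pairs: C(90,2) = 4005. For a given two-arm contrast:

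- one value from each of those arms: 30 × 30 = 900 pairs (22%), shift 2d/30
- one value from the third arm: 60 × 30 = 1800 pairs (45%), shift d/30
- both in the same arm: 3 × C(30,2) = 1305 pairs (33%), shift 0

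At 2d/30 the shift is 20/30 = 0.67 for d = 10 and 40/30 = 1.33 for d = 20. The standard error of an arm difference is SD × √(2/30), which is 2.07 at SD 8 and 3.10 at SD 12. The ratios are 0.67/3.10 = 0.22 to 0.67/2.07 = 0.32, and 1.33/3.10 = 0.43 to 1.33/2.07 = 0.65. One swap stays below one standard error.

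**3. Values re-sorted across arms.** With k of 90 values permuted, the expected share of the arm difference that remains is 1 − k/90:

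- k = 10: 1 − 10/90 = 0.89, a loss of 11%
- k = 15: 1 − 15/90 = 0.83, a loss of 17%

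Simulated contiguous blocks gave 0.89 and 0.84. With a true effect of 0.8 SD and a two-sided t-test at 0.05, simulated power falls from 86% to 77% with 10 values misplaced, to 49% with 30, and to 5% with all 90. A repeat run gave 75%, 48% and 5%.

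**4. Values re-sorted within arms.** If a fraction f is permuted, the correlation becomes r(1 − f). At f = 1/9:

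- change-score variance ratio, (1 − r(1 − f))/(1 − r): 0.556/0.5 = 1.11 at r = 0.5; 0.289/0.2 = 1.44 at r = 0.8
- baseline-adjusted residual variance ratio, (1 − r²(1 − f)²)/(1 − r²): 0.802/0.75 = 1.07 at r = 0.5; 0.494/0.36 = 1.37 at r = 0.8

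**5. Side check on precision.** For integer scores with an assumed mean of 30 and SD of 10, one 1-point error is missed on both summaries in 81% of cases at n = 90 if they are compared at one decimal, and in none at two decimals. Small value errors are therefore a concern only if the comparison is coarse.

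**The case against.** The best counter-argument is that checking is rolling. Data are to be cleaned as they arrive and compared weekly or monthly, and 3.m puts randomization at about 5 participants a month. A swap made at entry between participants entered in different intervals should show at the earlier check. With 18 monthly batches of 5, same-batch pairs number 18 × C(5,2) = 180, or 180/4005 = 4.5% of all pairs. This stands as a limit on how many swaps could go unseen. It hardly changes the split by arm: a complete block of 6 with two per arm has 15 pairs, of which 4 (27%) lie between the two contrasted arms, 8 (53%) involve the third and 3 (20%) lie within an arm. Nor does it cover a column put out of order after entry.

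Second, the larger effects rest on a hypothetical event. No section describes a sorting step, and re-sorting whole rows with their IDs does no harm. Damage needs a column detached from its IDs, in the database that is exported. That is correct, and no likelihood can be taken from the documents.

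Third, 3.p.2 speaks of several checking methods, and 3.p.2 and 3.p.3 mention cleaning separately. But the methods are those of 3.O, and no cleaning procedure is given. The other controls do not compare the two databases record by record: IDs on form pages and form review (3.n.2), double scoring and the change log (3.O), query resolution (3.r).

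Fourth, if both investigators paste from the same mis-sorted file, a cell-by-cell comparison also passes. That limits the remedy but does not support the present check.

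**Conclusion.** The concern holds. The stated reconciliation rule cannot detect values moved between participants within a variable and visit, and no other section supplies a record-level match. This part needs no assumption about arm size, SD or effect.

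The practical size depends on the error. A single swap is small, under one standard error in the range examined and zero for unadjusted arm means in about a third of pairs. A misaligned block or column can noticeably dilute a treatment effect or inflate residual variance while the check reports agreement. Those larger figures are illustrations under the assumptions listed, not a claim that such errors have occurred. The gap should be closed because the remedy is cheap and the failure would be silent. The monthly/weekly conflict is a minor inconsistency.

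**What to change.** In 3.O (Data Editing), 3.p.2, 3.p.3 and the matching roster row, replace the mean/SD comparison with wording such as: *The two databases will be compared cell by cell, matched on participant ID, visit and variable. Every mismatch will be listed and resolved against the source form or file.* State one frequency in all places, repeat the comparison before database lock, and say which database is exported for analysis. Means and SDs can stay as a plausibility check.

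The cost is a short comparison script on two databases that are already planned, plus time to resolve queries. Errors made identically in both databases would still need a check against source.

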### **3.0.1 External Data**

The only external data that will be collected in this study will be Kellgren-Lawrence Score which will determined by [name] from Radiographs that are stored in each patients medical record. These data will be requested from [name] by supplying each patient’s name and date of birth. [name] will provide the study team with a value for both knees which will be used for stratification prior to randomization into a treatment group.

## **3.p Quality Control**

### **3.p.1 Standard Operating Procedures**

The Sports Medicine Research Laboratory (SMRL), directed by [name], will be the site for data collection and analysis. All questionnaire data collected in the clinic will be immediately brought returned to the clinic. Participant research folders with signed consent forms will be located in locked cabinets. File drawers of these cabinets will be locked at all times and only study personnel will have access to keys that will open these drawers. All electronic data will be saved on password protected computers which will only be accessible to the study team. All Investigators will comply with all ethical standards that are mandated by the University of North Carolina IRB. The PI in study procedures, methods for data collection, data entry, and consenting procedures will train all study personnel.

### **3.p.2 Data and Forms Check**

Data will be checked using several methods including the data entry, data editing and data updating that have been outlined in section 3.O. We will use a double data entry technique and clean data as it becomes available in the Info Track databases. Means and standard deviations will be checked weekly to determine that the double data entry databases provide the same values for central tendency and variability for all outcome measures. Two separate investigators, using a Microsoft Excel calculation spreadsheet, will calculate outcomes from forms. Versions of forms and spreadsheets will be evaluated every time data is entered into the spreadsheets or when forms are provided to the patients.

### **3.p.3 Data Double Entry**

We will use a double data entry technique and clean data as it becomes available in the Info Track databases. Means and standard deviations will be checked weekly to determine that the double data entry databases provide the same values for central tendency and variability for all outcome measures. Two separate investigators, using a Microsoft Excel calculation spreadsheet, will calculate outcomes from forms.

### **3.p.3 Clinical Monitoring**

[name] will use visit the Meadowmont Physical Therapy Clinic on a monthly basis and observe the administration of the therapeutic exercises that are detailed in section 3.g. [name] will determine and document if the Physical Therapists are complaining with the descriptions of the exercises and dictating treatment progressions correctly. These monitoring procedures have been described in 3.m.

### **3.r Study Completion and Closeout Procedures**

#### ***Types of Study Close-out***

The two types of closeouts include a scheduled closeout, which occurs upon completion of the trial and an unscheduled closeout which may occur as a result of failure to obtain continuation funding, negative or positive findings, findings in other studies that impact on the clinical trial, or other unforeseen events. [name] is responsible for ensuring the following activities are completed prior to study close-out along with the Participant Close-out Procedures described below.

#### ***Study Forms***

- All outstanding Case Report Forms (CRFs) should be collected, organized, and any corrections made, where necessary.
- All data queries should be corrected and resolved.

#### ***Safety Reporting***

- All adverse events (both serious and non-serious) should be recorded and followed up to resolution in accordance with procedures detailed in the protocol.
- All serious adverse events (SAEs) should have been reported to the Data and Safety Monitoring Board (DSMB) or Safety Officer, Institute, Institutional Review Board (IRB), and other organizations, as specified in the protocol and Safety Monitoring Plan.

- All adverse events should have been reported as specified in the protocol.

### ***Study Files***

The investigator's study files should be complete and up-to-date with originals of the following maintained in the Study Binder, as relevant:

- Investigators Curriculum Vitae(s) (CVs), Investigator's Brochure(s) as relevant
- IRB approval letters for the protocol, all amendments, Informed Consents, annual reviews and advertisements (including updated approvals)
- IRB membership list
- All IRB correspondence
- Signature log
- TENS logs
- Copy of randomization code for randomization
- All informed consents should be signed and on file.
- Record retention procedures should be documented with respect the seven-year length of retention outlined in the manual of operating procedures.

### ***Clinical Supplies***

- Donjoy Global, who supplied the EMPI Select TENS units will be notified of the end of the study and TENS units will be shipped back to the company.

### **3.r.1 Participants Notification**

After all data for main outcome measures are calculated and published in peer-reviewed publications we will notify participants about the main finding of the study with a summary publication electronically mailed or mailed through the United States Postal Service (determined via participant preference). The study site should prepare a letter that thanks each study participant and could include the following information:

- Study findings
- Treatment assignment, as relevant to patients in the TENS + TE or the Sham TENS + TE group
- Treatment options, as relevant, whether continued treatment (TENS + TE or TE only) is indicated, and how and where treatment may be obtained
- Rights to confidentiality, privacy, and to no further contact from study staff, if that is participant's preference
- Subsequent updates or new and important information regarding knee osteoarthritis treatment
- Contact information of study staff

A copy of the letter should be included in the participant's file.

